### 9.2 Analysis Populations

#### 9.2.1 Safety Analysis Population:

The safety analysis population is defined as all patients who are randomized. Participants will be analyzed as treated.

#### 9.2.2 Intent-to-treat Population:

The intent-to-treat (ITT) analysis population is defined as all randomized patients. All efficacy analyses will be performed in the ITT population. Patients will be analyzed as randomized.

#### 9.2.3 Interim Analysis

It is understood that the underlying standard of care for COVID-19 patients is constantly improving and thus the estimates determined in this study are subject to change from published values utilized to determine the sample size. Thus, there is one planned interim analysis to be conducted after 150 total patients have completed the Day 28 visit. This will be conducted at an alpha level of 0.001, and thus the overall alpha level for the final test will be performed at  $\alpha=0.047$  instead of  $\alpha=0.05$ . The sponsor also reserves the right to alter the final sample size if the assumptions of clinical improvement are not satisfied at this interim analysis.

The interim analysis uses the same hypothesis test described in the final analysis where  $\mu_A$  and  $\mu_S$  represent the mean changes in the ordinal scale for Ampion and control respectively. Then, it is desired to demonstrate that the mean change for Ampion is different than the corresponding mean change for the control, respectively. Formally, this is presented as:

$$H_0: \mu_A = \mu_S \quad \text{versus} \quad H_A: \mu_A \neq \mu_S$$

The difference between Ampion and Placebo with respect to the change from baseline at Day 5 and Day 28 will be tested utilizing a Wilcoxon rank-sum test. To assess any potential time trends, an exploratory repeated measures analysis of variance will be performed with terms for treatment, time, and the interaction between the two.

The interim analysis is planned near the end of enrollment, after 150 patients, to test the protocol assumptions and estimates for clinical improvement, all-cause mortality rates and secondary endpoints as the available information and nature of the COVID-19 pandemic is rapidly evolving, which may impact estimates for both Ampion and control. The interim analysis will be used to determine if the sample size should remain at the planned 200 patients or increased based on the results of this analysis.

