## 4 SELECTION OF PARTICIPANTS

### 4.1 Number of Participants

The trial is designed for approximately 200 patients across two treatment arms (active or control), with a 100 subjects per arm, randomized 1:1 using a random allocation sequence stratified by COVID-19 disease severity (severe or critical).

The number of participants is selected based on the effects observed for the primary endpoint, all-cause mortality. A study in the New England Journal of Medicine with over 4,000 patients receiving the standard of care (SOC) for COVID-19 found a 26% mortality rate at Day 28 (njem 384;8, February 25, 2021). There was a similar observation in the Ampion Phase I study (AP-014) for patients with respiratory distress due to COVID-19 with a mortality for the SOC control arm of 21% by Day 28. In the AP-014 study, a lower mortality rate (8%) was observed for subjects receiving inhaled Ampion. Assuming the same proportions of deaths (8% for Ampion and 26% for control) by Day 28, the number of subjects (n=200) achieves at least an 80% power.

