## 9.4 Study Endpoints

### 9.4.1 Primary Endpoint

The primary endpoint assesses the effect of Ampion compared to placebo on clinical improvement. Clinical improvement is measured as the change in ordinal scale from baseline through Day 5 and Day 28.

Let  $\mu_A$  and  $\mu_S$  represent the mean changes in the ordinal scale for Ampion and control respectively. Then, it is desired to demonstrate that the mean change for Ampion is different than the corresponding mean change for the control, respectively. Formally, this is presented as:

$$H_0: \mu_A = \mu_S \quad \text{versus} \quad H_A: \mu_A \neq \mu_S$$

The difference between Ampion and Placebo with respect to the change from baseline at Day 5 and Day 28 will be tested utilizing a Wilcoxon rank-sum test. To assess any potential time trends, an exploratory repeated measures analysis of variance will be performed with terms for treatment, time, and the interaction between the two.

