7. INTERIM ANALYSIS AND EARLY STOPPING GUIDELINES

7.1 Interim Analysis

The interim analysis is planned near the end of enrollment, after 150 patients, to test the protocol assumptions and estimates for clinical improvement, all-cause mortality rates and secondary endpoints as the available information and nature of the COVID-19 pandemic is rapidly evolving, which may impact estimates for both Ampion and control. The interim analysis will be used to determine if the sample size should remain at the planned 200 patients or increase based on the results of this analysis.

The interim analysis will be conducted on the primary and secondary endpoint data at an alpha level of 0.001, and thus the overall alpha level for the final test will be performed at $\alpha=0.047$ instead of the nominal value of $\alpha=0.05$. The sponsor also reserves the right to alter the final sample size if the assumptions of clinical improvement are not satisfied at this interim analysis.

The interim analysis uses the same hypothesis test described in the final analysis where μ_A and μ_S represent the mean changes in the ordinal scale for Ampion and control respectively. Then, it is desired to demonstrate that the mean change for Ampion is different than the corresponding mean change for the control, respectively. Formally, this is presented as:

$H_0: \mu_A = \mu_S$ versus $H_A: \mu_A \neq \mu_S$

The difference between Ampion and Placebo with respect to the change from baseline at Day 5 and Day 28 will be tested utilizing a Wilcoxon rank-sum test. To assess any potential time trends, an exploratory repeated measures analysis of variance will be performed with terms for treatment, time, and the interaction between the two.

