7.2 Blinding Controls at Interim Analysis

The interim analysis will involve unblinded data. Only a small, sequestered team will have access to the unblinded data and results. The data will not be transferred, or results viewed by any person involved in the day-to-day conduct of the clinical trial, including, but not limited to the blinded sponsor staff, Medical Monitor, and/or blinded CRO staff. These individuals will remain blinded to the results.

The unblinded team will be responsible for obtaining the required material for the analysis from the study's unblinded data manager (DM) for the clinical trial. The unblinded team will present the results of the interim analysis to the sponsor in a blinded fashion (e.g., a simple recommendation to increase sample size or keep sample size as defined in the SAP without presenting details surrounding the raw data, results, or efficacy conclusions).

All individuals on the sequestered team who are unblinded will be documented and archived by the sponsor.

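### Sample size may change after an unblinded look with no written rule, maximum or combination test, so the intended 5% error is not guaranteed

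*Protocol*

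**What the plan says.** Protocol 9.2.3 sets the timing: "there is one planned interim analysis to be conducted after 150 total patients have completed the Day 28 visit". On the error level it says: "This will be conducted at an alpha level of 0.001, and thus the overall alpha level for the final test will be performed at" 0.047 in place of 0.05. SAP 7.1 repeats both levels. The interim applies the same Wilcoxon comparison of Ampion with placebo as the final analysis, and SAP 7.2 states: "The interim analysis will involve unblinded data".

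SAP 7.1 says the look serves to "determine if the sample size should remain at the planned 200 patients or increase based on the results of this analysis"; Protocol 9.2.3 says the same. Both sections then add a wider right: "The sponsor also reserves the right to alter the final sample size if the assumptions of clinical improvement are not satisfied at this interim analysis".

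Under SAP 7.2 a small sequestered team sees the results and passes the sponsor only a recommendation to keep or increase the size.

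SAP section 4 specifies the final test as a rank-sum test in PROC NPAR1WAY, with no stage weights. Neither document gives a maximum N, a re-estimation formula, a conditional-power zone, a combination statistic or a conditional-error argument. Nor is any ordinal-scale effect stated that could fail to be met: Protocol 4.1 and 9.1 and SAP 2.4 size the trial on Day 28 mortality of 8% against 26%.

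**The concern.** When the second-stage size depends on the observed interim effect, the pooled Wilcoxon statistic no longer has its usual null distribution. The direction of the change matters. Enlarging the trial after a weak interim dilutes a poor first stage and raises the chance of a false positive. Enlarging it after a promising interim lowers that chance. The written trigger, unmet assumptions of clinical improvement, points to weak results.

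At stake is whether the final p-value and confidence interval can be read at the level the plan sets. An extension after a disappointing look would be open to challenge, and a rule written after the look could not answer it.

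**Working it through.** **Inputs.** Interim at 150 patients and two-sided levels 0.001 and 0.047 (Protocol 9.2.3, SAP 7.1); planned N = 200, 1:1 (Protocol 4.1). The hypothesis is two-sided (Protocol 9.4.1), and I take the 0.001 as two-sided too. The critical values are 3.2905 at the interim and c = 1.9863 at the end. The caps and change rules below are assumptions, because the documents give none.

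**Model.** Z1 is the interim z-score and Z2 that of the later patients. For final size N the ordinary statistic is approximately

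Z = √(150/N)·Z1 + √((N−150)/N)·Z2.

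Given Z1 = z, the null chance of ending significant in favour of Ampion is

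e(z, N) = 1 − Φ[(c − √(150/N)·z) / √((N−150)/N)],

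and the other side mirrors it. Overall error = 0.001 + the integral of both sides over |z| < 3.2905, weighted by the standard normal density.

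**The plan's own figure.** With N fixed at 200 the overall error is 0.0470. The final level that would use up 0.05 exactly is 0.04998 (0.049 by Bonferroni). So 0.047 is conservative and leaves about 0.003 unused. The documents do not derive it.

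**Why direction matters.** Conditional error in favour of Ampion:
- z = 1.0, N = 200: (1.9863 − 0.8660)/0.5 = 2.241, giving 0.0125.
- z = 1.0, N = 400: (1.9863 − 0.6124)/0.7906 = 1.738, giving 0.041.
- z = 2.0, N = 200: (1.9863 − 1.7321)/0.5 = 0.508, giving 0.306.
- z = 2.0, N = 400: (1.9863 − 1.2247)/0.7906 = 0.963, giving 0.168.

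**Rules.** Conditional power (CP) at N = 200 under the observed trend is

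CP(z) = 1 − Φ[(c − √0.75·z)/0.5 − z·√(50/150)].

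It reaches 50% at z = 1.72 and 80% at z = 2.08. *Symmetric* means |z| is used, so a strong trend towards placebo also counts as high CP. The first three rules raise N to the cap.

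| Assumed rule | Cap 250 | 300 | 400 | 600 |
|---|---|---|---|---|
| Raise only if CP is 50–80% (symmetric) | 0.045 | 0.044 | 0.042 | 0.041 |
| Raise if CP for Ampion < 80% | 0.0497 | 0.0512 | 0.0529 | 0.0545 |
| – of which benefit side (nominal 0.025) | 0.0261 | 0.0276 | 0.0292 | 0.0307 |
| Raise if symmetric CP < 80% | 0.052 | 0.055 | 0.0585 | 0.061 |
| Theoretical maximum, increase only | 0.054 | 0.059 | 0.064 | 0.070 |

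With no cap the theoretical maximum is 0.083.

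**Check on real Wilcoxon statistics.** 400,000 simulated null trials were run with tie correction on an assumed nine-category distribution. A variant symmetric rule, choosing N to reach 80% CP, gave 0.052, 0.056, 0.061 and 0.067 at the four caps. The normal formula gives 0.053, 0.056, 0.061 and 0.066.

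**After the fix.** The statistic √0.75·Z1 + √0.25·Z2 has the same null distribution whatever N is chosen. At 0.001/0.047 its overall error is 0.0470. The Wilcoxon simulation gave 0.0466 to 0.0477 for caps of 250 to 600.

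**The case against.** The strongest reply is that no rule is written, so no error rate can be called broken. The plan also holds back about 0.003, and several rules the text allows stay within 5%: no change, an increase only at conditional power of 50–80%, or an increase to 250 for every result with directional conditional power below 80% (0.0497). This stands. A reader might infer that the 5% level is in fact lost and the final p-value invalid; the documents do not support that.

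The wording about clinical improvement is also directional, which favours the 0.050–0.055 row over the symmetric one. That stands too, although nearly all of the excess then falls on the benefit side. The maxima of 0.064 and 0.083 need a team that picks the most damaging N for every interim result, which neither document describes.

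A reader might also infer that the sponsor acts on unblinded results. SAP 7.2 answers this: the sponsor receives only a recommendation. That protects the conduct of the trial, but it does not change the null distribution of a pooled statistic whose size depends on Z1.

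A reader might take *alter* as planning a reduction. The surrounding text and SAP 7.2 speak only of keeping or increasing, so this is a loose word and not a planned option.

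Finally, this is Phase II. But the plan divides alpha between two looks and tests secondary endpoints hierarchically, so it does claim error control.

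**Conclusion.** The concern holds as a lack of guarantee. The plan permits a size change driven by the unblinded effect, keeps an ordinary final test and writes nothing that bounds the consequence. The realised two-sided error for one endpoint could be anywhere from about 0.041 to 0.061 under the fixed-increase rules examined, depending on a rule nobody has stated. The stated trigger leans towards the inflating end. The 0.003 held back does not reliably cover this: even a cap of 250 gives 0.052 under the symmetric rule.

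These figures rest on assumed caps and rules, a two-sided 0.001, an interim at exactly 150 of 200 and a normal approximation supported by simulation. They leave out the separate question of testing both Day 5 and Day 28. The point should be settled before the interim data are unblinded.

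**What to change.** In SAP 7.1 and Protocol 9.2.3, before the interim:

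- State that the final test combines the Wilcoxon z-score of the patients in the interim analysis with that of all later patients (inverse-normal, Cui–Hung–Wang), with weights fixed at √0.75 and √0.25, at the plan's own 0.047. Overall error is then 0.047 whatever N is chosen.
- State a maximum N and an increase-only rule, held by the sequestered team.
- Replace *alter* with keep or increase, to agree with the rest of 9.2.3 and with SAP 7.2.

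Two alternatives are acceptable: a pre-written cap and conditional-power zone shown to hold 5% with the ordinary test, or re-estimation from blinded pooled data only.

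The cost is wording, plus a small loss of efficiency if N is increased. For illustration, take an effect with 80% power at 200, so the mean of Z is 1.9863 + 0.8416 = 2.828. At N = 400 the ordinary statistic has mean 2.828 × √2 = 4.00 and power 97.8%. The weighted one has mean 0.75 × 2.828 + 0.5 × 2.828 × √(250/200) = 3.70 and power 95.7%. If N stays at 200 the two tests are practically the same.

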## **9.3 Data presentation**

### **9.3.1.1 Demographic and Baseline Characteristics:**

Demographic (e.g., age, sex, race, ethnicity) and baseline characteristics (e.g., weight, height, comorbidities) summarized using descriptive statistics, overall and by treatment group for the ITT and safety analysis population.

### **9.3.1.2 Medical History and Physical Examination:**

The number and percent of participants with past and current medical disorders at the time of randomization will be presented overall and by treatment group for the ITT and safety analysis population.

### **9.3.1.3 Concomitant Medications or Treatments:**

The number and percent of subjects receiving concomitant medications or therapies prior to and during the study and at the final visit will be tabulated and presented overall and by treatment group for the ITT analysis population.

Concomitant medications/treatments will be summarized using descriptive statistics and will be presented by type of drug (WHO DRUG classification) overall and by treatment group for the safety and ITT analysis populations. There should be no significant differences in the use of concomitant treatments between groups. All concomitant therapies will be recorded to be able to compare any inadvertent imbalances between the groups.

### **9.3.1.4 Safety Data:**

Safety data will be presented by treatment arm. Safety data will be evaluated by changes in vital sign measurements, laboratory assessments, and the frequency and severity of AEs. Concomitant medication will be recorded for safety. AEs will be collected from baseline to Day 60. The severity of AEs (mild, moderate, severe), relatedness (related, possibly related, unrelated) along with the duration, action taken, and outcome (e.g., study withdrawal) will also be recorded.

All data collected under this study protocol will be included in the assessment of patient safety. Missing or incomplete AE data will assume greatest relationship to study drug and/or severity.

Remaining safety data will be collected from enrollment through index hospitalization until hospital discharge (or in-hospital death). Safety data will be tabulated and presented overall and by treatment group for the safety analysis population.

### 9.3.1.5 Efficacy Data:

The efficacy of treatment on the clinical course and outcome of COVID-19 will be evaluated by comparing to placebo. Summaries will be performed by severity (severe or critical), individually, and combined.

Unless otherwise specified, continuous variables will be summarized with the number of non-missing observations, mean, standard deviation, median, minimum, maximum, and 95% confidence intervals displayed. Categorical data will be summarized as counts, percentages, and 95% confidence intervals.

## 9.4 Study Endpoints

### 9.4.1 Primary Endpoint

The primary endpoint assesses the effect of Ampion compared to placebo on clinical improvement. Clinical improvement is measured as the change in ordinal scale from baseline through Day 5 and Day 28.

Let  $\mu_A$  and  $\mu_S$  represent the mean changes in the ordinal scale for Ampion and control respectively. Then, it is desired to demonstrate that the mean change for Ampion is different than the corresponding mean change for the control, respectively. Formally, this is presented as:

$$H_0: \mu_A = \mu_S \quad \text{versus} \quad H_A: \mu_A \neq \mu_S$$

The difference between Ampion and Placebo with respect to the change from baseline at Day 5 and Day 28 will be tested utilizing a Wilcoxon rank-sum test. To assess any potential time trends, an exploratory repeated measures analysis of variance will be performed with terms for treatment, time, and the interaction between the two.

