## 1 PROTOCOL SUMMARY

### 1.1 Protocol Synopsis

Sponsor: Ampio Pharmaceuticals, Inc.	Investigational Product: Ampion™						
Title of Study:  A Randomized, Double-Blinded, Placebo-Controlled Phase II Study to Evaluate the Safety and Efficacy of Inhaled Ampion in Adults with Respiratory Distress due to COVID-19							
Rationale:  The severe acute respiratory syndrome coronavirus 2 (SARS-CoV-2) has resulted in the pandemic spread of coronavirus disease 2019 (COVID-19), which has a high rate of infection, has a high rate of hospitalization, has overwhelmed healthcare systems, and can be fatal.  Ampion is the low molecular weight filtrate of human serum albumin with the in vitro ability to modulate inflammatory cytokine levels. Ampion has the potential to improve clinical outcomes for COVID-19 patients by reducing inflammatory cytokines correlated with the disease and respiratory complications, such as Acute Lung Injury (ALI) and Acute Respiratory Distress Syndrome (ARDS).  This study aims to evaluate the effects of Ampion on mortality and clinical outcomes in patients with respiratory distress due to COVID-19. The data from this study will inform decisions for the clinical development of Ampion.							
Number of Sites:  Approximately 20 sites							
Indication:  Adults with respiratory distress due to COVID-19							
Number of Participants:  Sample size is approximately 100 participants per treatment arm							
Treatment Groups:  There are two planned treatment arms randomized 1:1, active to control:  

Treatment Arm	Investigational Treatment	

Active	Ampion for 5-days	

Control	Placebo for 5-days	

		Treatment Arm	Investigational Treatment	Active	Ampion for 5-days	Control	Placebo for 5-days
Treatment Arm	Investigational Treatment						
Active	Ampion for 5-days						
Control	Placebo for 5-days						

Sponsor: Ampio Pharmaceuticals, Inc.	Investigational Product: Ampion™
Objectives and Endpoints:	
Objective	Endpoint
Primary	
Assess the effect of Ampion compared to placebo on clinical improvement	

Change in ordinal scale from baseline through Day 5.

Change in ordinal scale from baseline through Day 28.

Secondary	

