### 9.4.2 Secondary Endpoints

Secondary endpoints assess the effect of inhaled Ampion treatment compared to placebo on the clinical outcomes for participants with respiratory distress due to COVID-19. The secondary endpoints will be tested in a hierarchical manner in the order presented, and thus no adjustment to the alpha level is necessary:

Objective	Endpoint
Secondary	
Assess the effect of Ampion compared to placebo on safety	

Incidence of adverse events (AEs) and serious adverse events (SAEs) from baseline to Day 60.

Assess the effect of Ampion compared to placebo on clinical health	

Change in NEWS2 score from baseline through Day 5.

Change in NEWS2 score from baseline to hospital discharge.

Objective	Endpoint
Assess the effect of Ampion compared to placebo on hospital stay	
 
Hospital length of stay (LOS) from admission to discharge.
 

Assess the effect of Ampion compared to placebo on oxygen use	
 
Change from baseline in oxygen use, blood oxygen saturation, and oxygen flow rate from baseline through Day 5.
 

Assess the effect of Ampion compared to placebo on progression to respiratory failure	
 
Percentage of participants who progress to respiratory failure (i.e., need for mechanical ventilation, ECMO, non-invasive ventilation) by Day 28.
 

Assess the effect of Ampion compared to placebo on intensive care	
 
Percentage of participants who require Intensive Care Unit (ICU) admission by Day 28.
 
ICU-free days through Day 28.
 
ICU LOS from ICU admission to discharge.
 

Assess the effect of Ampion compared to placebo on all-cause mortality	
 
Percentage of participants with a successful outcome (life) or unsuccessful outcome (death) by Day 28.
 

The efficacy endpoints will be evaluated to estimate the treatment effect and use descriptive statistics including mean, standard deviation, percentages, minimum/maximum, and 95% confidence intervals. All endpoints will be tabulated and presented by treatment arm, cohort (moderate and severe), and timepoint. Where appropriate, data will be tabulated and presented cumulatively across cohorts and/or timepoints.

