3. STUDY ENDPOINTS AND COVARIATES

3.1 Primary Endpoint:

The primary endpoint assesses the effect of Ampion compared to placebo on clinical improvement. Clinical improvement is measured as the change in ordinal scale from baseline through Day 5 and Day 28.

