4. HYPOTHESES

The primary endpoint assesses the effect of Ampion compared to placebo on clinical improvement. Clinical improvement is measured as the change in ordinal scale from baseline through Day 5 and Day 28.

Let μ_A and μ_S represent the mean changes in the ordinal scale for the three time points for Ampion and control respectively. Then it is desired to demonstrate that the mean change for Ampion is different than the corresponding mean change for the control, respectively. Formally, this is presented as:

$$H_0: \mu_A = \mu_S \text{ versus } H_A: \mu_A \neq \mu_S$$

The difference between Ampion and Placebo with respect to the change from baseline through Day 5 and Day 28 will be tested utilizing a Wilcoxon rank-sum test via PROC NPAR1WAY. To assess any potential time trends, an exploratory repeated measures analysis of variance will be performed with terms for treatment, time, and the interaction between the two. This will be done utilizing PROC GLM with the REPEATED option.

Secondary endpoints assess the effect of inhaled Ampion treatment compared to placebo on the clinical outcomes for participants with respiratory distress due to COVID-19. The secondary endpoints will be tested in a hierarchical manner in the order presented, and thus no adjustment to the alpha level is necessary:

Objective	Endpoint
Secondary	
Assess the effect of Ampion compared to placebo on safety	
Incidence of adverse events (AEs) and serious adverse events (SAEs) from baseline to Day 60.
Assess the effect of Ampion compared to placebo on clinical health	
Change in NEWS2 score from baseline through Day 5.Change in NEWS2 score from baseline to hospital discharge.
Assess the effect of Ampion compared to placebo on hospital stay	
Hospital length of stay (LOS) from admission to discharge.
Assess the effect of Ampion compared to placebo on oxygen use	Change in baseline in oxygen use, blood oxygen saturation, and oxygen flow rate from baseline through Day 5.
Assess the effect of Ampion compared to placebo on progression to respiratory failure	Percentage of participants who progress to respiratory failure (i.e., need for mechanical ventilation, ECMO, non-invasive ventilation) by Day 28.

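### Day 5 and Day 28 are both primary under one undivided final level of 0.047, and no rule says which pattern of results counts as success

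*Protocol*

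**What the plan says.** The primary section of the synopsis has two bullets, one for Day 5 and one reading "Change in ordinal scale from baseline through Day 28". Protocol 3.3.1 and 9.4.1 and SAP 3.1 and 4 instead speak of a single primary endpoint: "Clinical improvement is measured as the change in ordinal scale from baseline through Day 5 and Day 28".

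Both documents give one null and one two-sided alternative hypothesis on mean change, without attaching them to a day. The test in Protocol 9.4.1 is that the "change from baseline at Day 5 and Day 28 will be tested utilizing a Wilcoxon rank-sum test"; SAP 4 repeats it as "change from baseline through Day 5 and Day 28 will be tested utilizing a Wilcoxon rank-sum test via PROC NPAR1WAY". SAP 4 also defines the mean changes over three time points, although it names only Day 5 and Day 28. The repeated-measures analysis in the same sections is labelled exploratory, so it does not supply a single confirmatory test.

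On error control, Protocol 9.2.3 sets 0.001 for the interim look, and "thus the overall alpha level for the final test will be performed at" 0.047; SAP 7.1 says the same. The only ordering rule is in Protocol 9.4.2, repeated in SAP 4: "The secondary endpoints will be tested in a hierarchical manner in the order presented, and thus no adjustment to the alpha level is necessary". SAP 9.6 adds that the secondary efficacy analyses receive no multiple comparison adjustment, and says nothing about the two primary days.

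**The concern.** A rank-sum test on each day's change gives two primary p-values, and the plan gives one level to read them against. If one day is significant and the other is not, the documents cannot say whether the trial met its primary endpoint. That decision would then be made with the results in hand. If a one-day result is called a success with 0.047 used for each day, the error rate exceeds the level that the plan states.

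The gap carries into the secondary endpoints. A hierarchy holds the error only if the step before it is defined, and here it is unclear whether secondary testing opens after one significant day or two.

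**Working it through.** **Inputs from the documents.** Two primary days (synopsis; Protocol 9.4.1; SAP 3.1 and 4). Two-sided alternative (Protocol 9.4.1; SAP 4). Interim level 0.001 after 150 of 200 patients, so information fraction 150/200 = 0.75, and final level 0.047 (Protocol 9.2.3; SAP 7.1).

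**Assumed input.** The documents give no correlation between the Day 5 and Day 28 test statistics. It is taken as 0 to 0.95. Zero is an unlikely limit, because both changes subtract the same baseline score.

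**1. The plan's own level.** For a single endpoint, 0.001 at information fraction 0.75 followed by 0.047 gives an overall two-sided error of 4.70%. Against 5% that leaves 5.00 − 4.70 = 0.30 percentage points, too little to cover a second primary day. The plan's other figure, at least 80% power, also reproduces (92.9% at 0.05 and 92.6% at 0.047, for 8% versus 26% with 100 per arm). It concerns Day 28 mortality, now a secondary endpoint, and has no bearing on the two-day question.

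**2. Error under each possible rule.** The critical value is c = z(1 − 0.047/2) = 1.9863. Under the null on both days:

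P(either) = P(|Z5| > c or |Z28| > c) = 2 × 0.047 − P(both).

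At correlation 0, P(both) = 0.047² = 0.0022 and P(either) = 1 − (1 − 0.047)² = 0.0918. The other columns come from the bivariate normal distribution; the Hochberg row comes from 4 million simulated trials.

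| Rule, 0.047 | ρ = 0 | 0.5 | 0.7 | 0.9 | 0.95 |
|---|---|---|---|---|---|
| Either day counts, 0.047 on each | 9.2% | 8.6% | 7.9% | 6.6% | 6.1% |
| Both days required | 0.2% | 0.8% | 1.5% | 2.8% | 3.3% |
| Hochberg across the two days | 4.7% | 4.5% | 4.3% | 3.9% | 3.9% |
| Fixed sequence | 4.7% | 4.7% | 4.7% | 4.7% | 4.7% |

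The both-required row is for no effect on either day. If one day has a real effect and the other has none, the rate rises to at most 4.7%. The either-day rate comes down to 4.7% only at correlation 1.

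**3. Does the interim look matter?** Adding the 0.001 look on both days changes the either-day rate by less than 0.01 percentage point.

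**4. Does the normal approximation hold for an ordinal score?** Tie-corrected Wilcoxon tests on simulated change scores (assumed category distributions, 100 per arm, 40,000 null trials) gave either-day rates of 9.1%, 9.0%, 8.6% and 7.8% at realised correlations of 0.01, 0.26, 0.51 and 0.76. Each day alone gave 4.5% to 4.9%.

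**5. Power cost.** Assume that each day alone had 80% power; the documents give no such figure for the ordinal scale. Requiring both days gives 68.7%, 71.3% and 75.0% at correlation 0.5, 0.7 and 0.9, a loss of 11.3, 8.7 and 5.0 points. Hochberg finds at least one day in 86.3%, 83.3% and 79.6%.

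**The case against.** The strongest reply is that the plan already means both days. The endpoint sections use the singular, join the days with *and*, and give one hypothesis pair. On that reading the error never exceeds 4.7%, and only a clarifying sentence is missing. No passage says that either day suffices. It can also be said that this is a Phase II study meant to inform further development.

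Part of this stands. A reader might infer from the two synopsis bullets that either day counts, and so that the plan runs at about 9%. The documents do not support that: they never adopt an either-day rule or state that 0.047 applies to each day, and 9.2% also needs a correlation of zero. Inflation is conditional on one reading.

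The reply does not close the gap. No passage states that both days are required, the synopsis lists them separately, and the hypothesis pair is tied to neither day. The both-days reading has its own cost in power, and the sample-size sections (Protocol 4.1 and 9.1, SAP 2.4) justify the number only on mortality. Phase II status weakens the point only in part, since the plan itself sets formal levels of 0.001 and 0.047.

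**Conclusion.** The concern holds as an unstated success rule for the primary endpoint. Depending on the reading, the same text gives a false-positive rate of about 8.6% to 6.1% (either day, 0.047 on each, correlation 0.5 to 0.95; 9.2% at the unlikely limit of zero) or at most 4.7% (both days). The correlation range and the per-day use of 0.047 are assumptions. What the documents do show is that the choice between readings is left open, that SAP 4 does not settle whether there are two primary time points or three, and that the start of secondary testing is undefined as a result. This bears on the trial's main conclusion and should be settled before unblinding.

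**What to change.** In Protocol 9.4.1 and SAP 4, before unblinding:

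1. Change the reference to three time points to the two named days, or name the third and include it in the rule. The figures above are for two days.
2. State one success rule:
   - Hochberg across Day 5 and Day 28 at 0.047: both are significant if both p-values are at or below 0.047; otherwise a day is significant only at or below 0.047/2 = 0.0235. Simulated error is 3.9% to 4.7%.
   - A fixed sequence at 0.047 with a named first day, the other tested only if the first is significant.
   - Both days required at 0.047.

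   An even split of 0.0235 per day would also hold the level (4.6% to 3.1% over correlation 0 to 0.95), but Hochberg rejects whenever the split does, and sometimes when it does not.
3. State that the secondary hierarchy opens only when both days are significant, and reconcile this with the sentence in SAP 9.6 on no adjustment. If it could open after one day, a real effect on that day alone would leave the other day and the first secondary test each open at 0.047: 1 − (1 − 0.047)² = 9.2% if the two are independent. The first secondary listed is adverse-event incidence, so that sum would mix an efficacy test with a safety test.
4. State that the interim makes no efficacy claim, or apply the same rule there at 0.001. SAP 7.2 suggests the former, since the sponsor is to receive only a recommendation such as to increase or "keep sample size as defined in the SAP without presenting details surrounding the raw data, results, or efficacy conclusions".

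The cost is a protocol amendment with the approvals in Protocol 10.3 and a SAP revision, with no new data. Protocol 3.4 already has the SAP approved before unblinding. A result on one day only may no longer count as success, and requiring both days would cost about 5 to 11 points of power under the assumption in step 5 of the working.
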